5.3 LIFESTYLE CONSIDERATIONS

5.3.1 Meals and dietary restrictions

- 1. Refrain from consumption of grapefruit, grapefruit juice or grapefruit-containing products from 3 days before the start of study intervention until after the final dose.
- 2. Blood samples (biochemistry, blood glucose, biomarkers, etc) will be collected at the beginning of the visit in fasted conditions (fast overnight [eat nothing and drink only water] for at least 8 hours before blood samples are taken).
- 3. Over-the-counter dietary supplements (eg, herbal remedies) or prescriptions, are permitted during the study period. The Investigator should consider substituting medications that have cataractogenic potential according to their Prescribing Information for noncataractogenic treatments, as appropriate.

5.3.2 Caffeine, alcohol, and tobacco

No specific restrictions are required.

5.3.3 Activity

No specific restrictions are required.

5.4 SCREEN FAILURES

Screen failures are defined as participants who consent to participate in the clinical study but are not subsequently enrolled. A minimal set of screen failure information is required to ensure transparent reporting of screen failure participants to meet the Consolidated Standards of Reporting Trials (CONSORT) publishing requirements and to respond to queries from regulatory authorities. Minimal information includes demography, screen failure reasons, eligibility criteria, and any SAE.

Participant number will remain the same for rescreened participants for every screening/rescreening event.

Rescreening is possible for participants who have lag phase between the end of the EFC15392 study and the Screening visit (Visit 0) in the LTS15823 study, in cases where the original screening failure was due to reasons expected to change at rescreening and based upon the Investigator's clinical judgment. The patient may be rescreened once, after consultation with the Sponsor, while the screening period is still open if a participant failed for reasons of a nonpermanent medical condition, such as an acute disease or an event that could be corrected or resolved in an acceptable timeframe.

If a patient had screen-failed during a regional or national emergency for reasons not related to eligibility, rescreening shall be permitted when the situation normalizes (provided the rescreening will be still within 6 months of the last dose of IMP (Visit 12 [Month 24]) administered in the EFC15392 study and after consultation with the Sponsor).

5.5 CRITERIA FOR TEMPORARILY DELAYING ENROLLMENT OR ADMINISTRATION OF STUDY INTERVENTION ADMINISTRATION

During a regional or national emergency declared by a governmental agency that results in travel restrictions, confinement, or restricted site access, if the site is unable to adequately follow protocol mandated procedures, contingency measures should be considered for enrollment or administration of study treatment. Contingency measures proposed in Appendix 9 (Section 10.9) should be considered for enrollment or administration of study intervention.

6 STUDY INTERVENTION(S) AND CONCOMITANT THERAPY

Study intervention is defined as any investigational intervention(s), marketed product(s), placebo, or medical device(s) intended to be administered to a study participant according to the study protocol.

6.1 STUDY INTERVENTION(S) ADMINISTERED

Study intervention(s)

Investigational medicinal product(s)

- Formulation: venglustat is provided in capsule formulation containing 15 mg of venglustat (active moiety). Venglustat is not approved in any territory.
- Route(s) of administration: oral.
- Dose regimen: 15 mg once daily.

Table 3 - Overview of study interventions administered

Intervention label	GZ402671 or SAR402671
Intervention name	Venglustat
Туре	Drug
Dose formulation	Capsule
Unit dose strength(s)	15 mg
Dosage level(s)	15 mg once daily
Route of administration	Oral
Use	Experimental
IMP or NIMP	IMP
Packaging and labeling	Venglustat will be packaged in blister packs. Packaging is in accordance with the administration schedule. The content of the labeling is in accordance with Good Manufacturing Practices (GMP) requirements and the local regulatory specifications and requirements.
Current/Former name(s) or alias(es)	Not applicable
Table 4 - Arms	and associated interventions

Venglustat may be supplied at the site or from the Principal Investigator (PI)/site to the participant via a Sponsor-approved courier company where allowed by local regulations and agreed upon by the participant.

Venglustat

Property of the Sanofi group - strictly confidential

Associated interventions (intervention label)

For a regional or national emergency declared by a governmental agency that results in travel restrictions, confinement, or restricted site access, contingency measures are included in Appendix 9 (Section 10.9).

6.1.1 Devices

Not applicable.

6.2 PREPARATION/HANDLING/STORAGE/ACCOUNTABILITY

- 1. The Investigator or designee must confirm appropriate temperature conditions have been maintained during transit for all study intervention received and any discrepancies are reported and resolved before use of the study intervention.
- 2. Only participants enrolled in the study may receive study intervention and only authorized site staff may supply or administer study intervention. All study intervention must be stored in a secure, environmentally controlled, and monitored (manual or automated) area in accordance with the labeled storage conditions with access limited to the Investigator and authorized site staff.
- 3. The Investigator, institution, or the head of the medical institution (where applicable) is responsible for study intervention accountability, reconciliation, and record maintenance (ie, receipt, reconciliation, and final disposition records).

Any quality issue noticed with the receipt or use of an IMP (deficiency in condition, appearance, pertaining documentation, labeling, expiration date, etc) must be promptly notified to the Sponsor. Some deficiencies may be recorded through a complaint procedure (see Section 8.3.9).

A potential defect in the quality of IMP may be subject to initiation of a recall procedure by the Sponsor. In this case, the Investigator will be responsible for promptly addressing any request made by the Sponsor, in order to recall the IMP and eliminate potential hazards.

Under no circumstances will the Investigator supply IMP to a third party (except for direct-to participant (DTP) shipment, for which a courier company has been approved by the Sponsor), allow the IMP to be used other than as directed by this clinical trial protocol, or dispose of IMP in any other manner.

6.3 MEASURES TO MINIMIZE BIAS: RANDOMIZATION AND BLINDING

This is a single-arm open-label study; therefore this section is not applicable.

6.4 STUDY INTERVENTION COMPLIANCE

When participants self-administer study intervention(s) at home, compliance with study intervention will be assessed at each visit. Compliance will be assessed by direct questioning, counting returned capsules, etc during the site visits and documented in the source documents and relevant form. Deviation(s) from the prescribed dosage regimen should be recorded.

A record of the quantity of venglustat capsules dispensed to and administered by each participant must be maintained and reconciled with study intervention and compliance records. Intervention start and stop dates, including dates for intervention delays and/or dose reductions will also be recorded.

6.5 DOSE MODIFICATION

Not applicable.

6.5.1 Retreatment criteria

Temporary treatment discontinuation because of suspected AEs may be considered by the Investigator. After close and appropriate clinical and/or laboratory monitoring, once the Investigator considers, according to his/her best medical judgment that the occurrence of the concerned event was unlikely due to the IMP, the safety of the participant is not affected, and if the selection criteria for the study are still met (refer to Section 5), treatment with the IMP may be re-initiated. For all temporary treatment discontinuations, duration should be recorded by the Investigator in the appropriate pages of the electronic case report form (eCRF).

6.6 CONTINUED ACCESS TO INTERVENTION AFTER THE END OF THE STUDY

Continued access to the study intervention after the end of the study will be handled according to the local regulations.

6.7 TREATMENT OF OVERDOSE

For this study, any dose of venglustat greater than 15 mg within a 24-hour time period will be considered an overdose.

Sponsor does not recommend specific treatment for an overdose.

In the event of an overdose, the Investigator should do the following:

- 1. Contact the Sponsor immediately.
- 2. Evaluate the participant to determine, in consultation with the Sponsor, whether study intervention should be interrupted or whether the dose should be reduced.
- 3. Closely monitor the participant for any AE/SAE and laboratory abnormalities until venglustat can no longer be detected systemically (at least 6 days).
- 4. Document appropriately in the eCRF.

6.8 CONCOMITANT THERAPY

A concomitant medication is any treatment received by the participant concomitantly to the IMP.

Concomitant medications should be kept to a minimum during the study. Furthermore, changes in concomitant medications should be kept to a minimum and only occur if considered to be absolutely necessary in the medical judgment of the Investigator. However, if these are considered necessary for the participant's welfare and are unlikely to interfere with the IMP, they may be given at the discretion of the Investigator and must be recorded in the eCRF.

Concomitant medications, including over-the-counter dietary supplements (eg, herbal remedies) or prescriptions, are permitted during the study period, except for tolvaptan use which is forbidden throughout the study and the medications listed in the following section.

The Medical Monitor should be contacted if there are any questions regarding concomitant or prior therapy.

6.8.1 List of forbidden concomitant medication

During the study treatment periods, the following medications are prohibited:

- Use of investigational medication in any other clinical study.
- Chronic use of strong or moderate CYP3A inducers or inhibitors.
- Tolvaptan.
- Polycystic Kidney Disease-modifying agents (eg, somatostatin analogues).
- Alpha-adrenergic receptor agonist glaucoma medications because they can worsen the vision of participants with cataracts.

Venglustat interruptions are permitted for those participants who require temporary use (≤2 weeks) of strong or moderate inhibitors or inducers of CYP3A (per the United States Food and Drug Administration [FDA] classification)

(http://www.fda.gov/Drugs/DevelopmentApprovalProcess/DevelopmentResources/DrugInteractionsLabeling) for the treatment of acute illness. Such medications must not be used on more than a total of 2 occasions (ie, up to 2 weeks per occasion for a maximum of 30 days of venglustat interruptions) during the study treatment periods.

Given nonclinical lens findings (see IB), a chronic regimen (ie, more frequent than once every 2 weeks) of the following medications is forbidden during the clinical trial:

- Corticosteroids:
 - May be used on a restricted basis in participants who require temporary use (≤1 week) for the treatment of any acute condition for which no appropriate substitute is found. Such medications must not be used on more than a total of 4 occasions (ie, up to 1 week per occasion) during the study treatment periods.
 - Participants with chronic skin diseases can use low and least potent (Class VI to VII) topical steroids. Application to eyelids and periorbital region should be avoided.
- Psoralens used in dermatology with ultraviolet light therapy.

- Typical antipsychotics.
- Amiodarone.
- Allopurinol.

The Investigator should consider substituting medications listed in the previous paragraphs and medications that have cataractogenic potential according to their Prescribing Information for noncataractogenic treatments, as appropriate.

Atypical antipsychotics are allowed.

Other medications which are unlikely to interfere with the PK or PD of the IMP or confound interpretation of the study endpoints are allowed as needed and discussed with the Investigator. However, doses of chronically administered medicines should be kept fixed during the trial if at all possible.

6.8.2 Rescue medicine

Not applicable.

7 DISCONTINUATION OF STUDY INTERVENTION AND PARTICIPANT DISCONTINUATION/WITHDRAWAL

7.1 DISCONTINUATION OF STUDY INTERVENTION

7.1.1 Permanent discontinuation

In rare instances, it may be necessary for a participant to permanently discontinue study intervention.

Definitive (permanent) intervention discontinuation is any treatment discontinuation associated with the definitive decision from the Investigator not to re-expose the participant to the IMP at any time during the study, or from the participant not to be re-exposed to the IMP, whatever the reason.

The participants who develop loss of 3 or more lines of BCVA in either eye due to posterior subcapsular cataract could be discontinued from study treatment if recommended by the DMC (if DMC will decide that benefit/risk ratio is not favorable for this participant).

If a participant experiences a 50% reduction in eGFR compared to the screening value on at least 2 occasions separated by a period of at least 30 days during the course of this trial, the participant will stop the treatment and alternative therapy will have to be discussed by the Investigator.

If a participant experiences a reduction in eGFR below 30 mL/min/1.73 m² at on 2 occasions separated by a period of 3 months during the course of this study, the participant will be discontinued from the study.

If a participant experiences a reduction in eGFR below 25 mL/min/1.73 m², a repeated test must be performed in 30 days. If eGFR result repeated in 30 days is below 30 mL/min/1.73 m², the participant will be discontinued from the study.

The following may be justifiable reasons for the Investigator or Sponsor to discontinue a participant from treatment.

Participant specific:

- The participant experiences 2 similar SAEs or 1 life-threatening SAE (assessed as related by the Investigator and/or the Sponsor).
- The participant meets criteria for Hy's law (confirmed alanine aminotransferase ALT >5 × ULN range or confirmed ALT >3 × ULN and bilirubin >2 × ULN).
- The participant becomes pregnant (see Appendix 4 [Section 10.4] and Section 8.3.5).

Trial specific:

- Any AEs, per Investigator judgment, that may jeopardize the participant's safety.
- Any use of prohibited concomitant treatment (see Section 6.8.1).
- At participant's request, ie, withdrawal of the consent for intervention.

Any abnormal laboratory value or ECG parameter will be immediately rechecked for confirmation (after 24 hours) before making a decision of permanent discontinuation of the IMP for the concerned participant.

See the SoA for data to be collected at the time of discontinuation of study intervention and follow-up and for any further evaluations that need to be completed.

Handling of participants after permanent intervention discontinuation

Participants will be followed-up according to the study procedures specified in this protocol up to the scheduled date of study completion, or up to recovery or stabilization of any AE to be followed-up as specified in this protocol, whichever comes last.

If possible, and after the permanent discontinuation of intervention, the participants will be assessed using the procedure normally planned for the last dosing day with the IMP.

All cases of permanent intervention discontinuation must be recorded by the Investigator in the appropriate pages of the eCRF when considered as confirmed.

Participants who prematurely and permanently discontinue IMP should complete rapidly (within 7 days) an end-of-treatment (EOT) assessment visit without MRI.

Investigator should ask participant who prematurely and permanently discontinued IMP to continue study visits for safety and efficacy assessments up to and including the last scheduled visit, if possible.

If the participant refuses to attend all scheduled visits, the Investigator should ask the participant to return to the site at 24 months (to have at least an MRI and blood sample for eGFR evaluation, as well as safety assessments performed).

Participants who withdraw from the study due to pregnancy should be followed-up throughout the pregnancy up to approximately 6 to 8 weeks beyond the estimated delivery date so that the outcome of the pregnancy is determined. Additional follow-up information may be requested about the baby until at least 1 year after the birth of the baby, due to potential risk of abnormalities not present at birth. See Appendix 4 for guidance.

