7.2 PARTICIPANT DISCONTINUATION/WITHDRAWAL FROM THE STUDY

- A participant may withdraw from the study at any time at his/her own request, or may be withdrawn at any time at the discretion of the Investigator for safety, behavioral or compliance reasons. This is expected to be uncommon.
- At the time of discontinuing from the study, if possible, an early discontinuation visit (with procedures identical to EOT visit without MRI) should be conducted, as shown in the SoA. See SoA for data to be collected at the time of study discontinuation and follow-up and for any further evaluations that need to be completed.
- If the participant withdraws consent for disclosure of future information, the Sponsor may retain and continue to use any data collected before such a withdrawal of consent.
- If a participant withdraws from the study, he/she may request destruction of any samples taken and not tested, and the Investigator must document this in the site study records.

If participants no longer wish to take the IMP, they will be encouraged to remain in the study.

The Investigators should discuss with them key visits to attend. The value of all their study data collected during their continued involvement will be emphasized as important to the public health value of the study.

Participants who withdraw from the study intervention should be explicitly asked about the contribution of possible AEs to their decision, and any AE information elicited must be documented.

All study withdrawals should be recorded by the Investigator in the appropriate screens of the eCRF and in the participant's medical records. In the medical record, at least the date of the withdrawal and the reason should be documented.

In addition, a participant may withdraw his/her consent to stop participating in the study. Withdrawal of consent for intervention should be distinguished from withdrawal of consent for follow-up visits and from withdrawal of consent for non-participant contact follow-up, eg, medical record checks. The site should document any case of withdrawal of consent.

Participants who have withdrawn from the study cannot be reallocated (treated) in the study. Their inclusion and intervention numbers must not be reused.

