8.3.5 Pregnancy

- Details of all pregnancies in female participants and female partners of male participants will be collected after the start of study intervention and until the follow-up visit (30 days after the last dose of IMP).
- If a pregnancy is reported, the Investigator will record pregnancy information on the appropriate form and submit it to the Sponsor within 24 hours of learning of the pregnancy.
- While pregnancy itself is not considered to be an AE or SAE, any pregnancy complication
 or elective termination of a pregnancy for medical reasons will be reported as an AE or
 SAE.
- Abnormal pregnancy outcomes (eg, spontaneous abortion, fetal death, stillbirth, congenital anomalies, ectopic pregnancy) are considered SAEs and will be reported as such.
- The participant/pregnant female partner will be followed-up to determine the outcome of the pregnancy. The Investigator will collect follow-up information on the participant/pregnant female partner and the neonate and the information will be forwarded to the Sponsor.
- Any poststudy pregnancy-related SAE considered reasonably related to the study
 intervention by the Investigator will be reported to the Sponsor as described
 in Section 8.3.4. While the Investigator is not obligated to actively seek this information in
 former study participants/pregnant female partner, he or she may learn of an SAE through
 spontaneous reporting.

• Any female participant who becomes pregnant while participating in the study will discontinue study intervention and will be withdrawn from the study.

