9.3.2 Primary endpoint

The primary endpoint is percent change in TKV based on MRI from the EFC15392 study baseline to 24 months of open-label extension study, in early treated and delayed-treated participants.

The primary estimand will be the difference (early venglustat versus delayed venglustat) in mean percent change in TKV from the EFC15392 study baseline to 24 months in the LTS15823 study, in all participants from the primary efficacy population, regardless of whether or not participants completed the LTS15823 treatment period (treatment policy strategy).

Percent change from the EFC15392 study baseline in TKV will be analyzed using a mixed effect model with repeated measures (MMRM). The MMRM will include percent change in TKV at the following time points:

- Month 18 in the EFC15392 study.
- Baseline in the LTS15823 study.
- Month 24 in the LTS15823 study.

Percent change in TKV at Month 1 and Month 9 in the EFC15392 study will not be included in the MMRM since TKV at these time points was only assessed in participants from Stage 1.

The MMRM will include fix effect of treatment group (early venglustat versus delayed venglustat), Mayo Imaging Classification (as per randomization stratification factor in the EFC15392 study: Class 1C versus 1D versus 1E), time point (as a categorical variable), treatment*time point interaction, Mayo Imaging Classification*time point interaction as well as the continuous fixed covariates of baseline TKV and the baseline-by-time point interaction.

This model will include an unstructured covariance matrix to model the within-participant errors. Parameters will be estimated using restricted maximum likelihood method. Denominator degrees of freedom will be estimated using Kenward-Roger approximation.

Within group mean percent change in TKV will be obtained from MMRM, using weights for each stratum (Mayo Class 1C, 1D, and 1E) equal to the observed proportion of participants in each stratum in the primary efficacy population (ie, "population weight"). The difference in baseline adjusted least-squares means will be used to compare the early venglustat group to the delayed venglustat group, at the 2-sided 0.05 level.

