The primary analysis will include all observed TKV data in participants from the primary efficacy population, regardless of whether or not participants completed the treatment period. Participants who prematurely and permanently discontinue IMP in the LTS15823 study will be requested to obtain an MRI scan at 24-month visit and their data collected after treatment discontinuation will be included in the primary analysis. All efforts will be made to minimize the amount of missing data.

In order to evaluate the robustness of the primary analysis, sensibility analyses will be performed and described in the SAP.

Secondary analysis

A secondary analysis will estimate the difference in mean percent change in TKV from baseline during the on-treatment period (while on treatment strategy). In this secondary analysis, TKV assessed more than 30 days after the last LTS15823 study IMP administration will be excluded from the analysis. The TKV assessed in enrolled but not treated participants will also be excluded from the analysis. Any missing data during the on-treatment period will be considered "at random" in this secondary analysis; therefore, no imputation will be required since the MMRM provides valid inference under missing at random assumption.

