The following contingencies may be implemented for the duration of the emergency (after Sponsor agreement is obtained) to make clinical supplies available to the participant for the duration of the emergency: the DTP supply of venglustat from the site where allowed by local regulations and agreed upon by the participant. The DTP supply of IMP is not contingent on availability of contemporaneous laboratory results or other study specific assessments.

Procedures to be considered in the event of a regional or national emergency declared by a governmental agency (where allowed by local regulations) if onsite visits are not possible:

- Telephone contacts are to be performed in place of an onsite study visits and per study protocol schedule. Essential data (that can be checked via interview to evaluate participant safety) to be captured via telephone contact and documented in the source records include, but is not limited to, AEs, SAEs, change in or new concomitant medications, urine pregnancy test results, IMP compliance, potential signs of depressed mood, complaints about changes in vision, vital signs (if participants can measure temperature and BP at home).
- Visit ePROs (questionnaires) should be completed by the participant in the eDiary as usual. eDiary data can still be checked online by the Investigator/site team prior to calling the participant to ensure any follow-up questions or findings can be discussed.
- If it is feasible and there is no additional risk for a participant from the hazard the led to declaration of national emergency, consider performing blood tests in local laboratories:
 - Blood chemistry: at the minimum blood creatinine, AST, ALT, eGFR calculated with CKD-EPI equation,
 - Complete blood count.
- Participants with a recent eGFR >45 mL/min/1.73 m², may continue IMP up to 6 months, without having an onsite visit.
- Participants with a recent eGFR ≤45 and >30 mL/min/1.73 m², may continue IMP up to 3 months, without having an onsite visit. Participant who are not be able to repeat eGFR in 3 months will have to interrupt the treatment. Temporary IMP discontinuation will need to be registered in IRT.
- Participants with a recent eGFR ≤30 and >25 mL/min/1.73 m², who are not be able to repeat creatinine in 30 days will have to interrupt the treatment. If eGFR result repeated in 30 days is below 30 mL/min/1.73 m², the participant will have to stop the treatment permanently.

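### Do the low-eGFR rules in Protocol Section 7.1.1 need rewording because they end study participation rather than treatment?

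*Protocol*

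**What the plan says.** Protocol Section 7.1 deals with discontinuation of study intervention; leaving the study has its own Section 7.2. Section 7.1.1 contains three eGFR rules:

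- A confirmed 50% reduction from the screening value: "the participant will stop the treatment and alternative therapy will have to be discussed by the Investigator".
- eGFR below 30 mL/min/1.73 m² "on 2 occasions separated by a period of 3 months during the course of this study, the participant will be discontinued from the study".
- eGFR below 25 with a 30-day repeat below 30: the consequence is again discontinuation from the study.

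Appendix 9 (Section 10.9), which applies only in a declared emergency, has a rule for values above 25 and up to 30: "If eGFR result repeated in 30 days is below 30 mL/min/1.73 m², the participant will have to stop the treatment permanently".

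Section 7.1.1 then describes what happens after permanent discontinuation of intervention: "Participants will be followed-up according to the study procedures specified in this protocol up to the scheduled date of study completion". Visits are to continue if possible. Failing that, the participant is asked back at 24 months for at least an MRI, an eGFR sample and safety assessments. For someone leaving the study, Section 7.2 says that "an early discontinuation visit (with procedures identical to EOT visit without MRI) should be conducted".

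The primary estimand in Section 9.3.2 applies "regardless of whether or not participants completed the LTS15823 treatment period (treatment policy strategy", and the same section adds: "Participants who prematurely and permanently discontinue IMP in the LTS15823 study will be requested to obtain an MRI scan at 24-month visit".

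**The concern.** The protocol knows the difference between coming off drug and leaving the study. Its pregnancy rule (Section 8.3.5) imposes both, in so many words: the participant "will discontinue study intervention and will be withdrawn from the study". So the phrase used in the two absolute eGFR rules cannot simply be assumed to be shorthand for stopping drug.

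A site that took it literally would end visits for participants whose eGFR had fallen lowest. Their Month 24 MRI and eGFR would then be missing for a reason tied to outcome, although the treatment-policy estimand was written to include them. TKV is the more exposed endpoint. Its MMRM conditions on earlier TKV, baseline TKV and Mayo class but has no on-study eGFR term. The eGFR model is less exposed, because of any two scheduled values three months apart at least one is a time point in that model.

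Entry requires only eGFR above 30, so some participants could start close to the trigger. How many cannot be estimated: the documents give neither the entry distribution of eGFR nor a rate of decline.

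**Working it through.** No figure in the plan bears on this point, so the check is textual, with one piece of timing arithmetic.

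**1. Consequence of each rule**

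| Rule | Where | Stated consequence |
|---|---|---|
| 50% fall, at least two occasions at least 30 days apart | Protocol 7.1.1 | Treatment stops |
| Below 30 twice, 3 months apart | Protocol 7.1.1 | Leaves the study |
| Below 25, 30-day repeat below 30 | Protocol 7.1.1 | Leaves the study |
| Above 25 and up to 30, 30-day repeat below 30 | Appendix 9, emergencies only | Treatment stops |

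Two of the three rules in Section 7.1.1 end in study exit and one in a treatment stop. The inconsistency is confirmed. Appendix 9 is a weaker comparator, because it starts from a different eGFR band and applies only in emergencies.

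**2. Does study exit necessarily mean lost data?** Not on the text as a whole.

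- Section 7.2 refers the reader to the Schedule of Activities for follow-up. There, note c of Section 1.3.1 and note d of Section 1.3.2 give anyone who stops drug early a combined end-of-treatment/early-withdrawal visit and a visit 30 days after the last dose. The same notes request a Month 24 MRI after permanent discontinuation.
- The visit without MRI does not separate the two exits. Section 7.1.1 prescribes it for a treatment stop as well.
- Section 7.1.1 defines permanent intervention discontinuation to cover any definitive decision not to re-expose, regardless of cause. A participant removed under an eGFR rule also meets that definition, so the follow-up paragraph can be read as applying.

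Both readings remain open, but loss of the Month 24 data is not automatic.

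**3. Which reported results depend on the reading?**

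| Output | Status in the SAP | Depends on the reading? |
|---|---|---|
| Estimand; TKV; change in eGFR | Not applicable or not analysed (1.2.1, 4.3.1, 4.4.1) | No |
| Laboratory, ECG, eye and BDI-II analyses | Not done (4.7.3) | No |
| TEAE tables | Window ends 30 days after last dose (4.1, 4.7.2) | No; the 30-day visit applies either way |
| Exposure | First to last dose (4.7.1) | No |
| Non-completion of treatment | Reported with main reason (4.2) | No; drug stops either way |
| Non-completion of study | Reported with main reason (4.2) | Count no, reason possibly |
| Post-treatment deaths | Tabulated (4.7.2) | In principle, after the 30-day visit |

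The two disposition rows are not alternatives, and one participant can be in both. Protocol Section 4.4 counts a participant as completing the study only after 24 months of treatment and the Month 25 visit, so any early drug stop is a study non-completion too.

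**4. Timing.** The first participant enrolled on 09-Feb-2021. The SAP that records the decision to stop is dated 22-Jun-2021.

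- Days elapsed: 19 (rest of February) + 31 + 30 + 31 + 22 = 133.
- Month 24 is scheduled at Day 720, so the longest-followed participant was 720 − 133 = 587 days short.

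No Month 24 scan existed at that date. Early termination makes the participants non-completers whatever the eGFR wording says.

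**5. Size of what is left.** With 24 enrolled, one eGFR-triggered stop recorded under a different main reason moves 1/24 = 4.2% of participants between two lines of a descriptive table.

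**The case for a change.** The best argument for acting is that the contradiction is in the current protocol, that no sentence resolves it, and that resolving it costs only wording. The section heading makes loose drafting plausible, but plausibility does not instruct a site. The follow-up text in Section 7.1.1 is also partly a request, so a site that believed the participant had left the study would have little reason to pursue it. Had the trial run its course, the missing data would have been outcome-related and in conflict with the estimand.

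All of that stands as criticism of the drafting, and for a trial running to Month 24 with its planned efficacy analysis I would ask for the change. Three items are said to remain live after termination:

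- **Recorded reason for leaving the study.** This stands, at the size shown above. It is taken from the eCRF, and no SAP rule is needed to place the participant in a row.
- **End-of-study date.** The SAP defines an on-study period that uses it, but none of the analyses it specifies is based on that period.
- **Post-treatment deaths.** A death after the 30-day visit might be captured under one reading and missed under the other. This is possible in principle, among at most 24 people in a study that is closing for everyone.

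On the other side, a protocol amendment needs ethics committee approval before implementation (Section 10.1.1), which is hard to justify for a trial already being discontinued.

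**Conclusion.** The inconsistency is genuine. Section 7.1.1 uses two different consequences for similar eGFR triggers, and anyone reusing the text would have to reconcile them with the follow-up paragraph and, for emergencies, with Appendix 9. Which consequence should apply to which trigger is a clinical decision for the sponsor, and I take no view on it.

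No change to this plan follows, because there is nothing to gain. The analyses that literal compliance could have damaged have been withdrawn, the adverse-event tables are the same on either reading, and early termination makes participants non-completers in any case. The remaining effect is the reason recorded for a study exit, at 4.2% of participants for each case, plus a remote possibility concerning late deaths.

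This conclusion rests on two assumptions: that the early termination recorded in the SAP was carried out before anyone reached Month 24, and that the withdrawn TKV and eGFR analyses are not reinstated. If they were, the point would matter again.
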